The MethylationEPIC BeadChip (Illumina; San Diego, CA) will allow us to interrogate >800,000, methylation sites quantitatively across the genome at the Yale Center for Genome Analysis. A sample of pooled female DNA is routinely included on each BeadChip as a control throughout the experiment and assessed for reproducibility using a Pearson R² coefficient. We will set to missing data points with detection p-values >.001 and will exclude any samples with probe detection call rates < 95% as well as those with an average intensity value of either <50% of the experiment-wide sample mean or < 2000 arbitrary units (AU). To limit confounding due to positional effects, samples for each person will be run in the same row.

P16 Human p16 ELISA Kit (LSBio) will be used according to manufacturer's instructions.

***Stool collection:** A stool collection kit, collection and mailing instructions will be provided to each participant to collect a stool sample in their home as baseline, post chemo and 1-year. Stool will be returned by pre-paid Fed Ex delivery to the Yale School of Public Health. Samples will be frozen and then sent for analysis to outside laboratories (Metabolon and [name] at UCSD). Women who are randomized after their first chemotherapy session (but prior to their second session) will not be asked to complete the stool collection at baseline or thereafter as their stool microbiota may have been affected by the chemotherapy so change in microbiota would be uninterpretable.

Analysis of Chemotherapy Completion Rate: Chemotherapy completion rate will be assessed (via medical records in EPIC) as the average relative dose-intensity (RDI) for the originally planned regimen

based on standard formulas. We will measure the number and percent of patients requiring dose-adjustments, who have dose-delays, the reason for the dose-adjustment/dose delays (e.g. neuropathy or vacation) and the percent dose reduction for each participant and by group, similar to Courneya and van Waart's papers.(8, 9) All relevant data will be extracted from EPIC (electronic medical records).

Analysis of Pathologic Complete Response: Pathology reports will be used to evaluate residual tumor after neoadjuvant chemotherapy. Pathologic complete response will be defined as no evidence of viable invasive tumor cells at the primary tumor site and axillary lymph nodes in the surgical specimen, regardless of the presence of non-invasive breast cancer or DCIS (Tis); i.e., yT0/TisN0.

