In July 2020, all women who are or who have been (if they agreed to future contact as indicated on the study consent form) participants in LEANer will be invited via email to complete an online or hard copy survey regarding the effect of the coronavirus epidemic on their cancer care, and their mental health, diet and physical activity. A link to the survey, which will be hosted on the Qualtrics platform, will be included in the email invitation with instructions on how to get the hard copy questionnaire if desired. The survey will take approximately 10-15 minutes to complete. A study staff member will follow up by email, text message or phone to confirm receipt of the invitation to complete the survey and answer any questions.

Newsletter: A newsletter will be mailed to all participants at 6-monthly intervals while enrolled in the study informing them of the progress of the study and providing relevant information with regard to breast cancer survivorship issues.

All assessments denoted * above are conducted at the in-person visits and are optional.

d) Randomization: Participants will be randomized into one of 2 study arms using a random permuted block design of varying block size in a 1:1 ratio (N=125 to intervention, 125 to usual care). To ensure participants with similar characteristics are equivalently assigned to the 2 groups, we will stratify on the following factors that may be associated with some of the study endpoints:

- i) chemotherapy regimen (≤ 4 cycles vs. >4 cycles)
- ii) hormone receptor status (ER/PR+ or not)
- iii) HER2 status (HER2+ve or not)

Resulting in six strata.:

- a) HR/PR+ve, HER2-ve, ≤ 4 cycles
- b) HR/PR+ve, HER2-ve, >4 cycles
- c) HR/PR-ve, HER2-ve, ≤ 4 cycles
- d) HR/PR-ve, HER2-ve, >4 cycles
- e) HR/PR+ve, HER2+ve, >4 cycles
- f) HR/PR-ve, HER2+ve, >4 cycles

The following study personnel will be masked to participant study arm: clinic medical staff performing the DXA scan and laboratory analysis.

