Relative dose intensity will be calculated using the methods described by Longo et al [24]. The primary endpoint, RDI will be analyzed both as a continuous scale using the t test, and as a dichotomized outcome using 85% or 95% cut-off for Mantel-Haensel chi-square test controlling for stratification factors. In addition, group differences in chemotherapy completion rates will be analyzed with binary logistic regression analysis; whether or not having dose reduction during the period of chemotherapy treatment (the period between T0 and T1) will be the dichotomized dependent variable. The outcome of endocrine therapy adherence will be assessed at the 2 and 5-year follow ups (as most, if not all, participants prescribed endocrine therapy will have been taking it for at least 1 year at the 2-year visit, allowing us to assess adherence to endocrine therapy). The primary endocrine therapy outcome will be adherence to endocrine therapy assessed via the electronic medical records. Note: the assessment for the primary outcome of endocrine therapy adherence was changed from the initial assessment (urinary metabolites) as the COVID pandemic limited our ability to collect urine samples.

Secondary assessments of endocrine therapy will be:

a) Urinary AI level. An undetectable level will classify the participant as nonadherent to AIs.

b) Responses to the following questions:

(1) “In the past month, how often did you take your medications as the doctor prescribed?” Possible responses are all of the time (100%), nearly all of the time (90%), most of the time (75%), about half the time (50%), or less than half the time (<50%). Nonadherence is defined as 75% of the time or less.

(2) “In the past month, how often did you forget to take 1 or more of your prescribed medications?”

Possible responses were never, once in the past month, 2 to 3 times in the past month, once per week, several times per week, and nearly every day. Nonadherence is defined as forgetting to take prescribed medications once per week or more.

(3) “In the past month, how often did you decide to skip 1 or more of your prescribed medications?”

Possible responses were the same as for question 2. Nonadherence is defined as deciding to skip medications once per week or more. The first will be the primary measure of non-adherence. (73,74).

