Participants who report that they have discontinued taking tamoxifen or AI will also be classified as nonadherent to endocrine therapy. For patients who may be lost to follow-up, we will obtain prescription refill data as an endpoint of adherence to endocrine therapy. For the endocrine

therapy aim, we will compare the crude adherence rates using simple logistic regression. Multivariate logistic regression will serve as supportive analyses including covariate adjustments – which are similar to the primary analysis above.

The secondary aims will be performed using Mixed Model Repeated Measures analysis incorporating Analysis of Covariance, where each woman's changes in outcome (follow-up measure – baseline) will be modeled as a function of treatment and time with a covariate included for the baseline value. Prior to fitting models, we will perform exploratory data analyses focusing on the distributions of biological markers by time and intervention group, assessing the appropriateness of log-transformation.

All hypotheses will be tested according to the intention-to-treat philosophy in which all randomized participants will be grouped according to their intervention assignment at randomization, regardless of compliance or adherence to the study. Statistical significance will be defined as $p < 0.05$, 2-sided. Since we have multiple outcomes, we will consider using a Bonferroni correction.

Age, menopausal status, race/ethnicity, BMI at diagnosis, disease stage, type of surgery, type of chemotherapy, radiation therapy, hormone receptor status, endocrine therapy, reconstructive surgery, type 2 diabetes, and smoking status will be examined as covariates. We will explore effect modification by menopausal status at diagnosis, hormone receptor status, and endocrine therapy.

We will further explore intervention effects on study endpoints by stratifying by adherence to diet and physical activity guidelines with a four-level category (e.g., met diet recommendations, met physical activity, met both diet and physical activity recommendations, or met neither recommendation). This analysis will allow us to better understand the role of diet vs. exercise on study endpoints.

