Although we do not anticipate an appreciable number of subjects lost-to-follow-up because of our plan of following patients during their medical oncology visits, the impact of missing data will be evaluated in the analysis. Bivariate logistic regression will be used to identify baseline variables associated with missingness. The primary analysis assumes missing data are missing at random (MAR). Under the MAR missing data mechanism, the probability of loss-to-follow-up depends only on the observed data. Non-random or informative loss-to-follow-up occurs when the missing data are dependent on the unobserved missing outcome values, latent and/or instrumental variables. Sensitivity analyses using methods for NMAR data will be considered.

Power and Sample Size Considerations: The sample size estimate was performed using PASS 12 (©2013 NCSS, LLC, Kayesville, UT). The original calculation was based on chemotherapy completion rates reported in the COMPAS study (Ziller etc, BMC Cancer, 2013). By assuming similar completion rate in our control arm, we estimated a sample size of 250 subjects would be needed. Sample size reevaluation was conducted using the aggregated data of first 51 LEANer participants who completed chemotherapy. The pooled standard deviation of RDI is 0.10. We re-estimated that a sample size of 86 subjects per arm (172 total) will achieve 90% power to detect a 0.05 (or 5%) difference in RDI between two arms at significance level of 0.05. For endocrine therapy adherence, the COMPAS study reported 48% of patients in the control group were adhering to AI therapy at 12 months.¹⁸ We assume approximately 50% of patients randomized to usual care in our study will be adhering to endocrine therapy at one-year post-initiation of use. Group sample sizes of 76 patients per group (or $N = 152$) provides 90% power to detect an absolute difference of 25% in the intervention group (50% vs. 75%, adherence in control and intervention groups, respectively) at a two-sided 0.05 significance level. We anticipate ~70% of participants (i.e., 70% of 172 = 120) will be prescribed endocrine therapy; thus an $N = 120$ will also allow for sufficient statistical power.

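### Continuous RDI, the comparison the trial is sized on, is tested without the stratification factors used to randomize; the test is valid but conservative if those factors predict RDI

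*Combined protocol and SAP*

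**What the plan says.** Under Randomization (Section I, item 3d), allocation is 1:1 in permuted blocks, and the protocol says "we will stratify on the following factors that may be associated with some of the study endpoints". The factors are planned cycles (four or fewer versus more than four), hormone receptor status and HER2 status. They form six strata.

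Under Statistical Considerations (Section I, item 12), "RDI will be analyzed both as a continuous scale using the t test". The same sentence adds a dichotomized version at a cut-off of 85% or 95%, tested by a Mantel-Haenszel chi-square "controlling for stratification factors".

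The power paragraph rests on the continuous version: with an SD of 0.10, "a sample size of 86 subjects per arm (172 total) will achieve 90% power to detect a 0.05 (or 5%) difference in RDI".

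Two other statements in item 12 touch on adjustment. For endocrine therapy adherence, "Multivariate logistic regression will serve as supportive analyses including covariate adjustments". A list of covariates to be examined includes "type of chemotherapy, radiation therapy, hormone receptor status", but neither HER2 status nor number of cycles. No adjusted model is written down for continuous RDI.

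**The concern.** Blocking within strata makes the arms nearly equal on the stratification factors. If those factors predict RDI, the difference in means between arms varies less from trial to trial than it would under simple randomization. An unadjusted two-sample t test does not take account of this. It estimates its error from the total variance, between-stratum variance included, so its standard error exceeds the true one.

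The main result would then carry a wider confidence interval and a larger p-value than the design supports. This matters most if the true effect is smaller than the planned 0.05. The plan also treats its two RDI analyses differently without giving a reason.

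**Working it through.** **Inputs from the documents.** 86 women per arm, SD 0.10, difference 0.05, two-sided alpha 0.05 (item 12); 1:1 blocked allocation in six strata (item 3d).

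**Assumed.** R², the share of RDI variance explained by the strata, is not given. The values 0.05, 0.10, 0.20 and 0.30 are shown.

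**Step 1: the plan's own figure.** For an unadjusted two-sample t test with standardized difference 0.05/0.10 = 0.5, two-sided alpha 0.05 and 90% power, the noncentral t gives 85.03 per arm, rounded up to 86. Power at 86 per arm is 90.3%. The stated size is reproduced, and it belongs to the unadjusted test.

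**Step 2: standard errors.** The t test uses SE = 0.10 × √(2/86) = 0.01525. With strata balanced between arms, the true SE is 0.01525 × √(1 − R²), so the t test's SE is too wide by the factor 1/√(1 − R²).

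**Step 3: error rate and power.**
- True alpha of the t test: 2 × [1 − Φ(1.96/√(1 − R²))].
- Power of the t test: Φ[(0.05/0.01525 − 1.974)/√(1 − R²)], where 1.974 is the t critical value on 170 degrees of freedom.
- Power of the adjusted model: noncentral t with SD 0.10 × √(1 − R²) and 165 degrees of freedom.
- 95% CI half-width of the t test: 1.974 × 0.01525 = 0.0301, or 3.0 RDI points.

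| R² (assumed) | SE too wide by | True alpha, t test | CI half-width in RDI points, t test / adjusted | Power at 0.05, t test | Power at 0.05, adjusted |
|---|---|---|---|---|---|
| 0 | 0% | 5.0% | 3.0 / 3.0 | 90.4% | 90.3% |
| 0.05 | 3% | 4.4% | 3.0 / 2.9 | 91.0% | 91.7% |
| 0.10 | 5% | 3.9% | 3.0 / 2.9 | 91.5% | 93.0% |
| 0.20 | 12% | 2.8% | 3.0 / 2.7 | 92.8% | 95.4% |
| 0.30 | 20% | 1.9% | 3.0 / 2.5 | 94.1% | 97.4% |

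(At R² = 0 the normal form gives 90.4%, against the exact 90.3%.)

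At the planned effect, the power forgone runs from 0.7 to 3.3 points.

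**Step 4: a smaller true effect.** The same formulas with 0.04 in place of 0.05, for R² = 0.05, 0.10, 0.20 and 0.30, give about 75%, 75%, 77% and 78% for the t test, against 76%, 78%, 83% and 88% adjusted. The 0.04 is an assumption. The Background does show that effects below 0.05 are plausible: the cited three-arm exercise trial during adjuvant chemotherapy reports RDI of 84% in usual care, 87% with aerobic exercise and 90% with resistance exercise, so differences of 0.03 and 0.06. At 0.03 the t test stays at about 50%, while the adjusted model reaches 52%, 54%, 59% and 65%.

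**Step 5: simulation.** 10,000 trials per setting were run with permuted blocks of 4 or 6 in six strata. Assumed shares were 33% with four or fewer cycles (the protocol says about one-third), 72% receptor-positive (the protocol expects about 70% on endocrine therapy) and 17% HER2-positive (no figure in the documents). For the four R² values, t-test alpha was 4.8%, 3.6%, 3.1% and 2.1%. Power at 0.05 was 90.7%, 91.4%, 92.1% and 94.3% for the t test, against 91.4%, 92.9%, 94.9% and 97.5% adjusted. The adjusted model's alpha scattered around 5% (4.6% to 5.5%). The analytic table holds up.

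**The case against.** The strongest reply is that nothing breaks. The test is unbiased, its error rate does not exceed 5%, and the sample size was computed for this very test. That stands, and it makes this a point of efficiency and consistency, not of validity.

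The second reply is that R² is unknown and may be very small. RDI is defined as "average relative dose-intensity (RDI) for the originally planned regimen", which removes differences in planned amount, and the protocol says only that the factors may relate to some endpoints, without naming RDI. This also stands. At R² = 0.02 the true alpha is 4.8%, the half-width is 3.01 against 2.98 RDI points, and about 0.3 points of power are lost. Nothing in the documents supports the top of the range shown.

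The third reply is that adjustment is already intended. The sentence on supportive logistic models for adherence goes on to liken their covariate adjustments to those of the primary analysis, and the covariate list contains type of chemotherapy and receptor status. This does not settle the matter. The only continuous RDI analysis specified is the t test, the listed covariates are merely to be examined, and HER2 status and number of cycles are missing. The clause points back to a model that is not written down.

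A fourth reply is timing. The consent waiver text says genomic analysis was added after the relevant subjects were off study, so RDI data may already exist. That bears on how a change should be labelled, not on whether the analysis should match the design.

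**Conclusion.** The concern holds. The powered comparison of continuous RDI omits the factors on which randomization was stratified, while the dichotomized comparison in the same sentence includes them. The consequence is conservative: an interval and p-value somewhat larger than the design supports, with planned power intact at 90% or more. For R² between 0.05 and 0.30 the loss at the planned effect is 0.7 to 3.3 points of power, and up to about 10 points at an assumed true effect of 0.04 (78% against 88% at R² = 0.30). If the strata explain almost nothing, the two analyses agree. The sizes rest on the assumed R² and on near-balance within strata; the direction does not depend on the value chosen. The change is worth making because it costs almost nothing, but the trial's validity does not depend on it.

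**What to change.** State in item 12 that the primary analysis of continuous RDI is a linear model with arm and the randomization strata (cycles, receptor status, HER2 status), reporting the adjusted mean difference with its 95% CI. Keep the t test as a sensitivity analysis.

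For endocrine adherence, leave the crude comparison as planned. At most, name cycles and HER2 status as covariates in the supportive logistic model, and note that its odds ratio is conditional, not marginal.

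The cost is one sentence. The strata are recorded before randomization, the linear model estimates the same mean difference, and it uses at most five of the 170 residual degrees of freedom. If the strata explain nothing, about 0.1 point of power is lost. No change in sample size is needed. If RDI has already been compared by arm, the adjusted model should be reported as added after that comparison.

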- a. Does your YNHH privilege delineation currently include the **specific procedure** that you will perform? Yes No
- b. Will you be using any new equipment or equipment that you have not used in the past for this procedure? Yes No
- c. Will a novel approach using existing equipment be applied? Yes No

If you answered "no" to question 4a, or "yes" to question 4b or c, please contact the YNHH Department of Physician Services ([name]) for prior approval before commencing with your research protocol.

IMPORTANT REMINDER ABOUT RESEARCH AT YNHH

Please note that if this protocol includes Yale-New Haven Hospital patients, including patients at the HRU, the Principal Investigator and any co-investigators who are physicians or mid-level practitioners (includes PAs, APRNs, psychologists and speech pathologists) who may have direct patient contact with patients on YNHH premises must have medical staff appointment and appropriate clinical privileges at YNHH. If you are uncertain whether the study personnel meet the criteria, please telephone the Physician Services Department at [contact]. **By submitting this protocol as a PI, you attest that you and any co-investigator who may have patient contact has a medical staff appointment and appropriate clinical privileges at YNHH.**

SECTION I: RESEARCH PLAN

1. **Statement of Purpose:** State the scientific aim(s) of the study, or the hypotheses to be tested.

We propose to examine, in 172 women newly diagnosed with Stage I-III breast cancer who are not practicing the dietary and lifestyle guidelines, and who will receive neoadjuvant or adjuvant chemotherapy as part of their treatment, the effect of a 1-year dietary and physical activity guidelines intervention vs. usual care on the breast cancer outcomes described below. Women will be enrolled either before beginning chemotherapy or following the first chemotherapy infusion but prior to the second chemotherapy infusion (Time 0). Follow up visits will occur post chemotherapy (Time 1), at one-year post-diagnosis (Time 2), at two years post-diagnosis (Time 3) and at five years post-diagnosis.

Primary Endpoints: Adherence to Breast Cancer Treatments

Aim 1a: Chemotherapy completion rates (dose amount, number of dose reductions and dose delays)

Aim 1b: Adherence to endocrine therapy in women taking tamoxifen or Aromatase Inhibitors (AIs) at 12- and 24-months after enrollment

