How will adverse events and unanticipated problems involving risks to subjects or others be reported, reviewed and managed? The protocol represents minimal risks to the subjects and adverse events are not anticipated. Adverse events are defined as injury possibly associated with participation in the physical activity component of the intervention. In the unlikely event that a serious, unanticipated and related adverse event occurs, it will be reported in writing within 48 hours to the Yale HIC, DFCI IRB and within a week to the NIH. Yale study staff will inform DFCI study staff within 48 hours if they become aware of any adverse events occurring in patients enrolled at DFCI.

What provisions are in place for management of interim results? The Principal Investigator will evaluate the adverse events and study data at regular intervals (every quarter) and determine whether the adverse event affects the Risk/Benefit ratio of the study and whether modifications to the protocol or consent and authorization form are required.

What will the multi-site process be for protocol modifications? The Yale PI will inform the DFCI site of any protocol changes via email.

12. Statistical Considerations: Describe the statistical analyses that support the study design.

Statistical Analyses: Statistical analyses will be conducted by the Yale Center for Analytical Sciences, which provides extensive statistical support to Yale Cancer Center. Analyses will be performed using SAS v9.3. The statistical design is a two-armed, randomized intervention study. The primary objective is to examine the effect of the intervention on relative dose intensity of chemotherapy, adherence to endocrine therapy at 12- and 24-months, with the secondary aim of evaluating the intervention on biomarkers, body composition and quality of life.

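### RDI and endocrine adherence are both primary at the full 0.05 with no binding multiplicity rule: about 10% familywise error if either counts, or about 84% and 73% power if Bonferroni is applied

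*Combined protocol and SAP*

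**What the plan says.** **Which endpoints are primary.** The Statement of Purpose (Section I, item 1) puts Aim 1a, chemotherapy completion, and Aim 1b, endocrine adherence, under one label: "Primary Endpoints: Adherence to Breast Cancer Treatments". Statistical Considerations (Section I, item 12) opens with one primary objective that covers "relative dose intensity of chemotherapy, adherence to endocrine therapy at 12- and 24-months". The paragraph after that calls RDI the primary endpoint, in the singular, yet also states: "The primary endocrine therapy outcome will be adherence to endocrine therapy assessed via the electronic medical records".

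**How RDI is tested.** The analysis listed first keeps RDI on its own scale: "RDI will be analyzed both as a continuous scale using the t test". The second splits it at a threshold that is left open: "as a dichotomized outcome using 85% or 95% cut-off for Mantel-Haensel chi-square test controlling for stratification factors". A logistic model for any dose reduction is added. None of the three is labelled as the deciding analysis.

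**Error control.** Significance is set at two-sided 0.05. The only statement on multiplicity is: "Since we have multiple outcomes, we will consider using a Bonferroni correction". No family, split or order of testing is given. Power and Sample Size Considerations uses the full 0.05 for RDI and again for endocrine adherence.

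**Endocrine time points.** Aim 1b names 12 and 24 months after enrollment, and the primary objective in item 12 repeats those months. Further on, item 12 says: "The outcome of endocrine therapy adherence will be assessed at the 2 and 5-year follow ups". The power statement assumes adherence one year after therapy starts. Experimental Design (Section I, item 3a) places the 5-year follow-up after the initial primary results have been published.

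**The concern.** With two primary endpoints and no statement of whether one success is enough, whether both are needed, or which comes first, the plan does not define a positive trial. A correction that will only be considered can be adopted or dropped once the p-values are known.

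Either outcome has a cost that the plan does not state. Without a correction, and with success on either endpoint accepted, the false-positive risk for the primary claim is close to twice the nominal 5%. With a correction, the power figures no longer apply, because each was worked out at the full 0.05. The conflicting endocrine time points add a further open choice for the second endpoint.

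**Working it through.** **Inputs.** From Power and Sample Size Considerations: RDI SD 0.10, difference 0.05, 86 per arm, 90% power, alpha 0.05; endocrine adherence 50% against 75%, 76 per group for 90% power at two-sided 0.05; about 70% of 172, or 120 women, on endocrine therapy. From Randomization (Section I, item 3d): 1:1 allocation. Assumption: the 120 split evenly, 60 per group.

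**Step 1. Reproduce the plan's figures.**
- RDI: n = 2(1.960 + 1.282)² × 0.10²/0.05² = 84.1, so 85 per arm by the normal approximation. The t-test solution is 85.03, rounded up to 86. Power at 86 is 90.3%. The plan's figure is reproduced.
- Endocrine, pooled test: n = [1.960√(2 × 0.625 × 0.375) + 1.282√(0.5 × 0.5 + 0.75 × 0.25)]²/0.25² = 76.7, so 77 against the stated 76. Power at 76 is 89.7%. This agrees within rounding.

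Both calculations match only at the full 0.05.

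**Step 2. Familywise error if either endpoint counts.** 1 − (1 − 0.05)² = 0.0975 for independent tests. The ceiling is 0.05 + 0.05 = 0.10 for any dependence. The documents give no correlation between the two test statistics; if it were 0.1, 0.3, 0.5 or 0.7, the error would be 9.7%, 9.5%, 9.1% or 8.3%.

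**Step 3. Power if Bonferroni is applied (0.025 each).** Familywise error is 1 − 0.975² = 4.94% for independent tests.

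| Endpoint | Power at 0.05 | Power at 0.025 | n per group for 90% at 0.025 |
|---|---|---|---|
| RDI, 86 per arm, standardized difference 0.05/0.10 = 0.5 | 90.3% | 84.4% | 101 |
| Endocrine, 60 per group | 81.6% | 72.8% | 91 |

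Endocrine check at 60 per group: (0.25√60 − 1.960 × 0.6847)/0.6614 = 0.899, and Φ(0.899) = 0.816. With 2.241 in place of 1.960 the value is 0.608, and Φ(0.608) = 0.728. At 0.025 the RDI difference detectable with 90% power rises from 0.050 to 0.054.

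**Step 4. Fixed sequence, RDI first, each at 0.05.** Familywise error stays at 5% and RDI keeps 90.3% power. If both assumed effects are real and the tests are independent, the chance of reaching and winning the endocrine test is 0.903 × 0.816 = 0.737, about the same as the 72.8% under the split.

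**Step 5. Endocrine time points side by side.**

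| Place | Time point |
|---|---|
| Item 1, Aim 1b | 12 and 24 months after enrollment |
| Item 12, primary objective | 12 and 24 months |
| Item 12, endocrine outcome | 2 and 5 years |
| Item 12, power | one year after initiation |

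Year 2 is common to the first three. Item 12 explains that most women will have at least a year of therapy behind them by the 2-year visit, which ties that visit to the power assumption. What does not reconcile is 12 months on one side and 5 years on the other. A 5-year result also cannot belong to primary results that are published before the 5-year follow-up begins.

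**The case against.** The strongest reply is that RDI is already the lead. Item 12 calls it the primary endpoint in the singular, Analysis of Chemotherapy Completion Rate (Section I, item 3c) defines completion as average RDI, and the 172 is sized on mean RDI, with the endocrine subset then checked for adequacy. On that reading the t test on continuous RDI decides and the rest is supportive. This stands as evidence of intent for RDI. It does not remove the second primary, because items 1 and 12 both give endocrine adherence that status.

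A second reply is that chemotherapy delivery and later endocrine adherence are different questions in partly different women, so 5% each is defensible. That is fair, but the plan does not say it, and its own sentence on multiple outcomes treats the matter as open.

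Three stronger readings are tempting, and the documents do not support them.
- A reader might infer that the trial's error rate is 10%. That follows only if one success is enough, which no passage states. If both were required, there would be no inflation.
- A reader might infer that the open 85% or 95% cut-off inflates the primary error rate. Simulation of the stratified Mantel-Haenszel test under assumed RDI distributions and strata shares gives 8.3–9.6% when the better cut-off is chosen, but this matters only if the dichotomy decides. The text may equally mean that both cut-offs will be reported.
- A reader might take the remark that the endocrine covariate adjustments are ones "which are similar to the primary analysis above" as a sign that the Mantel-Haenszel test is primary, since a t test has no covariates. The remark concerns a logistic model, and the dose-reduction logistic regression is the closer parallel, so it is weak evidence.

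**Conclusion.** The point holds, and the plan should be changed. Two endpoints carry primary status, each uses the full 0.05, and no rule links them. If either counts, familywise error is about 9.75%, and at most 10% provided each test holds its 5% level. If Bonferroni is applied, power is about 84% for RDI and 73% for endocrine adherence, in place of about 90% and 82%. If the aims are separate questions, each keeps 5%, but this has to be written down.

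The power figures rest on the plan's own SD, difference and adherence rates, and on an even split of 120 women on endocrine therapy. The intended RDI analysis can be inferred as the t test, so the unfixed cut-off is a gap in specification and not a shown threat to the primary error rate. The endocrine time points conflict on their face, with year 2 as the common ground.

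**What to change.** 1. State that the t test on continuous RDI is the single primary RDI analysis. Label the dichotomy and the dose-reduction model supportive. Either fix one cut-off or report both. There is some support for 85%: the Background reports that threshold from an earlier exercise trial, and item 3c says the completion measures will be similar to that trial's.
2. Reconcile the endocrine time points and name one as primary. The 2-year visit is the one common to Aim 1b, the primary objective and the endocrine outcome text. State its anchor, since Aim 1b counts from enrollment and the visit schedule counts from diagnosis.
3. Replace the conditional Bonferroni sentence with a binding rule. The preferred one is a fixed sequence, RDI first and then endocrine adherence, each at 0.05. The alternative is 0.025 each, with power restated as about 84% and 73%. If the aims are instead declared separate questions at 0.05 each, say so and make no claim of trial success that rests on either one alone.

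**Cost.** A few sentences and no extra women. The fixed sequence costs RDI no power but allows no confirmatory endocrine claim if RDI fails. The split keeps both aims confirmatory at the lower power; restoring 90% would take 101 per arm for RDI and 91 per group on endocrine therapy, against 86 and about 60.

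Set the rule before any comparison by arm. The documents do not show whether one has been made. If it has, the rule can no longer be prospective, and the report should say that it was set afterwards.
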